
Aim 1: Demonstrate the feasibility of use of PENFS to treat PSH, and tolerability of the device. Hypothesis: The PENFS device will be well tolerated, defined as < 10% early termination from the study. We will recruit 20 patients with ASBI and PSH who will receive PENFS therapy.
 
Aim 2a: Evaluate the feasibility of capturing pediatric PSH symptoms using the CFS scoring tool. Hypothesis: It is feasible to monitor the severity of PSH using a CFS scoring tool (Table 1a,1b). The scoring tool will be adapted for the appropriate age range of the patient (Table 2). We aim for at least 80% scoring (<math>\geq 8/10</math> scheduled scoring per protocol while the device is worn).
 
Aim 2b: Evaluate the effectiveness of the PENFS device in reducing PSH symptoms using change in CFS score. Hypothesis: A decrease in CFS severity score with use of PENFS will be associated with a lower number and/or doses of maintenance and rescue medications for control of PSH symptoms.
 
Aim 3a: Evaluate the change in autonomic balance with use of PENFS device Hypothesis: Heart Rate Variability (HRV) and pupillometry parameters that correspond to sympathetic and parasympathetic activity will be different after PENFS device placement compared to before, reflecting an increase in parasympathetic tone. All patients will be on routine continuous EKG monitoring in the PICU during the study period of interest. Similarly, pupillometry is routinely performed in patients with ASBI in the PICU.
 
Aim 3b: Evaluate feasibility of measuring PENFS effectiveness in treating PSH by a decrease in medication use. Hypothesis: It would be feasible to use the maintenance and rescue medication dosing and frequency as a marker of severity of PSH. PENFS device use will result in lesser number and/or doses of maintenance and rescue medications for control of PSH symptoms. We will compare the pilot sample to a historical cohort to allow power analysis and sample size calculation for a future larger efficacy trial, recognizing that this pilot study is not powered for efficacy.

D. Background, significance, and rationale (including description of preliminary studies and any results):

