### **E. Design and methods (including experimental design, technical details and laboratory methodology):**

#### **Design & Methods**

In this prospective unblinded pilot study we will enroll eligible patients until 20 parent/child dyads complete the study. It is expected many of the consented patients will not meet the eligibility criteria of CFS score > 6 (moderate severity of PSH). Those children will be considered Screen Failures and their parents/LAR told they are ineligible to continue in the study. Children admitted to the PICU at CW aged 2-17 years with ASBI and symptoms of PSH with a CFS score > 6 (moderate severity of PSH) will be eligible for inclusion. Exclusion criteria include age < 2 years (small ears thus less surface area to apply the leads), ear deformity or severe dermatitis of ear lobes, intractable seizures, heart block, patients with other implantable devices (cardiac pacemaker, vagal nerve stimulator, etc.) or known pregnancy.

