### **Aim 1: Identify and enroll 20 pediatric patients with ASBI and PSH.**

**Methods:** Parent(s)/legal guardians, 18 years or older, will be approached for informed consent if their child has ASBI and is exhibiting clinical signs and symptoms of PSH. Once consented, the CFS scoring tool (Table 1a,) will be used to evaluate patients felt to be exhibiting symptoms of PSH to identify eligible ASBI patients. Patients with CFS score > 6 will be eligible for enrollment in the study.

Families of patients who do not meet the CFS score criteria > 6 will be told their child did not meet scoring criteria of study and will be considered consented but not enrolled in study.

Study Enrollment is defined as meeting CFS criteria of > 6 after consent. If CFS scores are already being collected for subject prior to subject consent as a standard of care, we can use already available CFS scores from medical record. The PENFS device will be placed over the external ear by study investigator or one of trained nurses (RNs) from the Pediatric Translational Research Unit (P-TRU) within 24 hours of meeting CFS > 6 score criteria..

There are 380-400 PICU admissions/year that are seen by ICU Neurology. Using a conservative estimate of 8-10% incidence of PSH, we expect to have 35-40 patients with PSH. At a conservative 60% enrollment rate, we expect to be able to successfully enroll 20 patients in this pilot study. Previous studies using the device has shown it to be well-tolerated with minimal side effects (25,26). In a large, randomized sham-controlled trial Kovacic et al showed a very low rate of discontinuation of the device due to side effects. We hypothesize that the dropout rate will be ≤ 10%. Tolerability of the device will be assessed by subjective assessments of device tolerance by the bedside nurse, the CFS score (increasing score after device placement would suggest worsening PSH symptoms) and skin integrity (bedside nurses will perform routine skin evaluation and care while the device is in place.). To evaluate safety, we will monitor for serious adverse effects such as cardiac dysrhythmia (EKG monitoring), and new-onset seizures.

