### Risks

**A. Describe potential research-related risks and discomforts (consider physical, psychological, legal, social/economic/financial, loss of confidentiality, group harms); describe the probability, magnitude, and duration of the potential risks; do not address risks that would be present if the individual did not participate:**

Local discomfort/pain, skin irritation. Theoretical risks include cardiac dysrhythmia and new-onset seizures neither of which have been reported in previous studies. In a randomized sham-controlled trial of the use of the device for 115 children with functional abdominal pain, only 1 patient among 60 with active device discontinued treatment due to discomfort, whereas 6 patients in the sham-group discontinued the device one being adhesive allergy. Patients will be monitored (including EKG monitoring at least in the initial 48 hours of the device) as inpatient during the time the device is in place. Other studies have also reported minimal to no side-effects using the device for other indications.

Other risks include remote possibility of loss of confidentiality if there is any breach of study data.

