## Protocol Summary/Submission Application

**B. If there is no formal DSMB/DMC, describe the monitoring plan or indicate that the study involves no more than minimal risk (if the IRB disagrees and determines the study to be greater than minimal risk, the study will be deferred until an appropriate monitoring plan has been developed):**

Members from the division of critical care (MD, APP) will meet every 2 months to review data on device safety. Any serious adverse event deemed related to study will be notified immediately for adjudication.

**C. Have stopping rules been established for the study (to evaluate whether the objectives have been met, or that the objectives cannot be met, or that the accumulated data indicates that the risks exceed the benefits of the study)?**

No  Yes  N/A (study is not greater than minimal risk)

If YES, describe the stopping rules:

Any symptomatic cardiac dysrhythmia or new-onset seizure deemed to be as a result of the device use.  
 5 consecutive patients showing device intolerance i.e worse comfort scores, worse CFS score,

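### The only tolerability stopping rule counts an unbroken run of 5 intolerant children, so it would rarely fire at intolerance rates of 20% to 50%; add a pause for review at 5 in total

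*Combined protocol and SAP*

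**What the plan says.** Section 6, item C gives two stopping rules. One is a symptomatic dysrhythmia or new-onset seizure attributed to the device. The other, and the only one about tolerability, is "5 consecutive patients showing device intolerance i.e worse comfort scores, worse CFS score". The printed list breaks off at a comma after the second item, so a further item may have been lost.

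Item B of the same section says that critical care clinicians "will meet every 2 months to review data on device safety". It gives no count or proportion at which they should pause or stop.

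Aim 1 hypothesises good tolerability. The aims section puts the limit at below "10% early termination from the study". The Aim 1 methods put it slightly differently: "We hypothesize that the dropout rate will be ≤ 10" per cent. The sample is a convenience sample of 20, and enrolment continues "until 20 parent/child dyads complete the study", so more than 20 may be treated.

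The Risks section reports earlier experience from a sham-controlled trial: "only 1 patient among 60 with active device discontinued treatment due to discomfort".

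**The concern.** A run rule ignores how many children have been intolerant overall and asks only whether the last five all were. After four intolerant children, one tolerant child returns the count to zero. In a study of about 20 children, such a rule can be expected to react only when nearly every child is intolerant.

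The children affected are those enrolled after a pattern of intolerance has appeared. Intolerance here includes a worse CFS score, meaning worse PSH, and the Background links PSH to secondary brain injury. The safety group would see the data, but nothing in the plan tells it to add up cases across meetings or at what number to pause.

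**Working it through.** The plan states no operating characteristics for the rule, so there is no figure to reproduce.

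**Inputs from the documents.** Run length 5 (Section 6, item C). Sample of 20 (Section 6, item D), counted as completers (Design & Methods). Expected accrual is 60% of 35 to 40 children with PSH a year (Aim 1 methods).

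**Inputs assumed.** The true intolerance rate *p* is not given, so a range is shown. Children are taken as independent with the same *p*.

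**Rule as written.** Let F(n) be the probability of at least one run of 5 within n children. Then F(n) = 0 for n < 5, F(5) = p^5, and for n > 5

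F(n) = F(n−1) + [1 − F(n−6)] × (1 − p) × p^5.

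At p = 0.5 this gives F(20) = 0.2499, which agrees with full enumeration of the 2^20 sequences (0.24987).

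**Count of 5 in total.** P(X ≥ 5) with X binomial(20, p).

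| Assumed rate | Run of 5 within 20 | 5 in total within 20 |
|---|---|---|
| 10% | 0.0001 | 0.043 |
| 20% | 0.004 | 0.37 |
| 30% | 0.028 | 0.76 |
| 40% | 0.10 | 0.949 |
| 50% | 0.25 | 0.994 |
| 60% | 0.48 | 0.9997 |
| 70% | 0.73 | above 0.999 |

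Solving for an 80% chance of firing gives p = 0.731 for the run and p = 0.313 for the total.

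**If intolerant children drop out and are replaced until 20 complete.** Each of the 20 completers is preceded by a string of intolerant children, which reaches length 5 with probability p^5. The run rule therefore fires with probability 1 − (1 − p^5)^20. At 30% this is 1 − (1 − 0.00243)^20 = 0.047; at 50% it is 1 − (1 − 0.03125)^20 = 0.47. The total rule becomes P(X ≥ 5) with X binomial(24, p): 0.085 at 10%, 0.89 at 30% and 0.999 at 50%. Replacement helps the run rule somewhat but leaves it weak at 30%.

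**Worst case.** With t tolerant children, at most 4(t + 1) intolerant children fit without a run of 5. For 20 children, t + 4(t + 1) ≥ 20 requires t ≥ 4 (3.2 rounded up), which leaves at most 16 intolerant. Only 70 of the C(20,16) = 4,845 orderings of 16 intolerant and 4 tolerant children avoid a run, or 1.4%.

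**Accrual against the review interval.** 35 × 0.6 = 21 and 40 × 0.6 = 24 children a year, so 3.5 to 4 per two-month interval.

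**The case against.** **The safety group already looks.** It meets about every four children whatever the count. At a 30% rate the fifth intolerant child arrives on average after 5/0.3 ≈ 17 children, by which time about four reviews have taken place; at 50% it arrives after about 10 children and two reviews. This stands. The gap is a missing written threshold, not missing oversight. Other protections also stand: a single device-attributed symptomatic dysrhythmia or seizure stops the study, skin and comfort are monitored, the device is easily removed, and rescue drugs are allowed throughout.

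**A run is a filter against noise.** CFS fluctuates with the disease, and the plan does not say how much worsening counts or when it is measured. If fluctuation alone raised CFS in an assumed 20% to 30% of children, a count of 5 in total would be reached with an inert device with probability 0.37 to 0.76. This also stands. It argues for a pause rather than an automatic stop, and for defining intolerance in the same amendment.

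**Stronger readings the documents do not support.**
- A reader might infer that 16 of 20 children could well be intolerant without a stop. Sixteen is a bound that needs a rare ordering. With 16 intolerant in random order, the rule fires 98.6% of the time.
- A reader might set the rule against the 10% limit in Aim 1 and call the two contradictory. That limit is a hypothesis about early termination or dropout. Worse comfort or CFS scores need not end participation, so the measures are related but different, and the limit is not a safety boundary.
- A reader might take "the accumulated data indicates that the risks exceed the benefits of the study" as a commitment by the sponsor to use cumulative data. The words belong to the review form's question, which lists it as one of several alternative purposes.
- A reader might credit a count of 5 in total with capping the intolerant children at 4 or reducing the average number exposed. That would hold only if the fifth case ended enrolment. After a pause the group may resume.

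**Conclusion.** The concern holds as a weakness in the stopping rule. At assumed intolerance rates of 30% to 50%, the only written tolerability stop stays silent with probability 0.97 to 0.75 over 20 children, and it becomes reliable only above about 70%. These figures rest on independence, a constant rate and a rate range that the documents do not supply. They also depend on what counts as intolerance, which the plan leaves open.

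If the list in item C was cut short, a lost item could change the rate at which children count as intolerant but not the visible requirement for five in a row. The earlier discontinuation rate for discomfort, 1 in 60, suggests that high intolerance is not expected, but it comes from children with functional abdominal pain and covers discomfort alone. The gap is worth closing because doing so is cheap; it does not show that children would go unmonitored.

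**What to change.** Keep the present rule as the stop and add one sentence to Section 6, item C: *Enrolment also pauses for review by the critical care group when 5 patients in total, consecutive or not, have shown device intolerance.* Any run of 5 is also 5 in total, so the pause can never come later than the existing stop.

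In the same amendment, complete the list. State whether a worse comfort score or a worse CFS score alone is enough, and name the post-placement CFS score to be compared with the score for the 12 hours before placement.

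The cost is one sentence and one definition, using the existing reviewers and data already collected. Treatment, schedule and sample size do not change. At a true rate of 10% the chance of an unneeded pause is 4%, or 8.5% if intolerant children are replaced. It is larger if CFS fluctuation alone counts, as shown above, and a pause delays a study expecting 21 to 24 children a year. The sponsor may prefer another count: 4 in total would be reached with probability 0.13 at 10% and 0.89 at 30%.

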**D. Describe procedures to be employed in analyzing data (including a power analysis):**

*This is a pilot feasibility study of use of the device. A convenience sample of 20 patients was chosen.*

### Section 7 Regulatory Criterion for Approval: Privacy and Confidentiality

**When appropriate, there are adequate provisions to protect the privacy of subjects and to maintain the confidentiality of data.**

- Privacy refers to persons and their interest in controlling access to themselves
- Confidentiality refers to agreements with the subject about how data are to be handled

**A. Provisions for the protection of privacy of subjects (having control over the extent, timing, and circumstances of sharing oneself [physically, behaviorally, or intellectually] with others):**

Every effort will be maintained to protect the privacy of subjects. Potential patients and their families will be approached in a private room in the PICU to discuss the study. If they agree, the consent process will also take place in this private room without interference from others. In addition, during the consenting process the subject of privacy surrounding the subject's data will be discussed.

Individuals will not be identified in scientific presentation of findings or in publications. The subject will have right to withdraw from study anytime by writing to study PI and any further data collection will be stopped beyond that point.

**B. Provisions to maintain the confidentiality of data (the treatment of information that an individual has disclosed in a relationship of trust and with the expectation that it will not be divulged to others in ways that are inconsistent with the understanding of the original disclosure, without permission):**

Every effort will be made to protect the confidentiality of patient's data. Their coded data, including a Study ID, will be entered into a password protected REDCap database for study analysis. A separate password protected Excel file will exist as a key to the coded data. It will contain the Study ID number along with some PHI such as MRNs. The MRN in this file is the PHI which serves as the key to the code. Both password protected files will be stored on the secured MCW secured servers and are only accessible by the study team.

## Protocol Summary/Submission Application

All research team members will be trained regarding human subject research and the confidentiality of data using the institution's standard, web-based CITI training modules and will possess appropriate CITI certification.

**C. If paper records are being maintained, indicate where paper documents will be kept and how secured (This includes hard copies of signed consent forms, as well as any other documents containing subject PHI):**

Any hard copy data forms will be assigned the appropriate Study ID. The data will be entered into the REDCap study database. The hard copies will be stored in a locked cabinet accessible only to the study team. A copy of the signed consent with HIPPA authorization will be maintained in patient's medical records at Children's Wisconsin.

**D. Describe whether data will be shared outside MCW/CW, with whom (include outside collaborators and their institutions), and how (anonymous, identifiable, coded, de-identified [review [OHRP guidance](#) if uncertain]):**

**If an investigator leaves MCW/CW during the study and the PI intends for the individual to continue to work on the study as a collaborator, this section must be updated and submitted as amendment package for IRB review. The CW HRPP will need to consider whether the investigator is conducting human subject research, whether data are appropriately protected, and whether a reliance agreement will need to be executed with the investigator's new institution.**

The only people allowed to handle subject's health information are those on the research team at CHW/MCW and those who check on research activities to make sure the hospital rules are followed.

**E. Will a Certificate of Confidentiality (CoC) be obtained for this research or is one already in place?**

*Certificates of Confidentiality are issued automatically when:*

- *Research is conducted or supported by NIH and falls within the scope of the NIH policy.*
- *Research is conducted or supported by the CDC and involves the collection of identifiable, sensitive information.*
- *Research is funded by the FDA in whole or in part and involves the collection or use of identifiable, sensitive information as defined in 42 U.S.C. 241(d).*

*If you need help in making the determination, contact the HRPP office at [contact].*

**No**    **Yes**    **N/A (study is not conducted, supported or funded by NIH/CDC/FDA)**

If YES, the required disclosure language must be included in the consent form(s) (see NIH [website](#) for suggested consent language).

### Data Security Provisions

**All research projects that collect electronic data must use appropriate security measures to ensure that data are protected from theft or loss in order to prevent breaches of confidentiality. You must indicate what encryption tools will be used from the options below, or indicate further below why they are not necessary.**

The IRB will not review this protocol unless you indicate the encryption tools being used to secure your research data. If you do not have encryption in place on your systems, contact your Information Management Systems support team to arrange for one of the encryptions options listed below.

The following encryption products employ cryptographic modules that the National Institute of Standards and Technology has certified as meeting FIPS 140-2 requirements. Children's Hospital and Health System endorsed the use of these products made to encrypt hard drives and removable media. All electronic research data must be encrypted using one or more of these products.

***This protocol summary/submission application must be kept current and revised via the amendment process for IRB approval if any security measures change during the course of the research study.***

## Protocol Summary/Submission Application

Indicate which encryption tools you are using to secure your research data:

**Key:** HD = Hard Drive; RS = Removable Storage (USB flash drive, CD, etc.); PD = Portable Device (iPod, iPhone, PDA, etc.)

	Credent Mobile Guardian (RS, PD)		McAfee Endpoint Encryption (HD, RS)
	GuardianEdge Hard Disk and GuardianEdge Removable Storage Encryption (HD, RS, PD)		Seagate Secure Self-Encrypting Drives (HD when encryption option is enabled)
	IronKey encrypted flash drives (RS)		Symantec Endpoint Encryption (HD, RS, PD)
	SafeNet Protect Disk and SafeNet Protect File (HD, RS)		WinMagic SecureDoc encryption (HD) (for MCW owned computers)
	Microsoft Bitlocker (HD, RS when used with Windows 7 and FIPS compliant algorithms are enabled)		PGP Whole Disk Encryption and PGP Portable (HD, RS)
	OTHER (describe): Click here to enter text.		

**NOTE: BOX is not a CW-approved tool for securing protected health information and cannot be used for research.**

Does not apply because:

	Data are de-identified – no PHI collected (provide detailed information on data elements in the protocol summary/submission application)		Data are stored on BOTH CW and MCW secured shared drives
	Data are stored on CW secured shared drives		Data are stored on paper only
	Data are stored on MCW secured shared drives		OTHER (describe): Password protected REDCap Database managed by QHS

### Section 8 Regulatory Criterion for Approval: Vulnerable Populations

**When some or all of the subjects are likely to be vulnerable to coercion or undue influence, such as children, prisoners, individuals with impaired decision-making capacity, or economically or educationally disadvantaged persons, additional safeguards have been included in the study to protect the rights and welfare of these subjects.**

Additional steps to minimize coercion and undue influence:

- Assessment of capacity
- Permission of a representative
- Assent
- Witness to the consent process

Subpart D—Additional Protections for Children Involved as Subjects in Research (FDA: In order to approve research in which some or all of the subjects are children, an IRB must determine that all research is in compliance with 21 CFR part 50, subpart D.)

A. Do you intend to enroll children as subjects?
Yes
B. What is the age range of the children in this research?
2-17 years

